# 9.2. Discussion of Study Design, Including Choice of Treatment Groups and Appropriateness of Measurements

This will be a randomized, double-blind, multicenter, parallel group, placebo-controlled safety and tolerability study in adults with ADHD. The target subjects are healthy male and female adults aged 18 to 64 years, inclusive, with a diagnosis of ADHD. 50 subjects will be randomized; assuming a 20% dropout rate, it is anticipated that 40 subjects will complete the study.

Blinding to treatment will be employed to reduce potential bias during data collection and evaluation of endpoints. Randomization will be used in this trial to avoid bias in the assignment of subjects to treatment, to increase the likelihood that known and unknown subject attributes (e.g., demographics and baseline characteristics) are evenly balanced across treatment groups, and to enhance the validity of statistical comparisons across treatment groups.

The primary objective of this Phase I/IIa study is to evaluate the safety of SPN-812V in these subjects. Safety will be assessed by the monitoring of AEs, vital signs, clinical laboratory tests, physical examinations, and ECGs.

The secondary endpoints of this study are:

- 1. To establish the efficacy of SPN-812V over a 5-week treatment period with SPN-812V 300 mg/day
- 2. To establish the initial efficacy of SPN-812V after a 1-week treatment period with SPN-812V 150mg/day.
- 3. To establish the effectiveness of SPN-812V over a 6-week treatment period with either SPN-812V dose.
- 4. To establish the clinical utility of SPN-812V after a 5-week treatment period with SPN-812V 300mg/day.
- 5. To establish the study subject's perception of clinical benefit of SPN-812V at endpoint after a 5-week treatment with SPN-812V at 300mg/day.

6. To explore in a population model the single-dose and steady state pharmacokinetics of SPN-812V in adults with ADHD.

To determine the drug effect on reducing ADHD symptoms, the CAARS will be utilized. The CGI Scale will be administered to reflect drug effect on global functioning. These efficacy assessments will be performed at all study visits. Subjects who have agreed to participate in the optional PK sub study will have the efficacy assessments performed prior to blood being drawn and dosing for the PK sub study.

Randomization will be used in this trial to avoid bias in the assignment of subjects to treatment, to increase the likelihood that known and unknown subject attributes (e.g., demographics and baseline characteristics) are evenly balanced across treatment groups, and to enhance the validity of statistical comparisons across treatment groups.

## 9.3. Selection of Study Population

This study population was selected to evaluate SPN-812V safety and efficacy in adults, aged 18 to 64 years old, inclusive, with ADHD. In this study 50 subjects will be randomized at approximately 5 US sites.

## 9.3.1 Inclusion Criteria

Subjects meeting all of the following criteria may be included in the study:

- 1. Able to provide informed consent prior to any study procedure being conducted.
- 2. Capable and willing to comply with study procedures.
- 3. Male or female aged 18 to 64, inclusive.
- 4. Subjects with a current diagnosis of ADHD as confirmed by the Conners' Adult ADHD Diagnostic Interview for DSM-IV (CAADID)
- 5. Clinical Global Impression Severity (CGI-S) score of 4 or higher.
- 6. On no treatment for ADHD or willing to be withdrawn from an ongoing treatment after a washout of at least 10 days.
- 7. Body Mass Index (BMI) between 18.0 and 34.0 inclusive
- 8. Subject must be in general good health as determined by medical history, ECG, and other analysis that, in the judgment of the Investigator, would confirm the Subject's good health.
- 9. Females of childbearing potential (FOCP) who, if sexually active, agree to use acceptable forms of contraception (including oral, transdermal, or implanted contraceptives; intrauterine device; female condom with spermicide; diaphragm with spermicide; cervical cap; abstinence; use of condom with spermicide by sexual partner or sterile [at least 6 months prior to SM administration] sexual partner) at least 14 days prior to start of study drug administration, throughout the study, and for 30 days following the last dose of SM.
- 10. Postmenopausal females with amenorrhea for at least 2 years or females who are permanently sterilized (e.g., tubal occlusion, hysterectomy, bilateral salpingectomy).

# 9.3.2 Exclusion Criteria

A subject will not be eligible for inclusion in this study if any of the following criteria apply:

- 1. Current or past history of psychotic disorder or major depressive disorder with psychotic features.
- 2. Presence of another primary DSM-IV-TR disorder.
- 3. Suicidality, defined as either active suicidal plan/intent or active suicidal thoughts in the 6 months before the Screening Visit or more than 1 lifetime suicide attempt. (The Columbia-Suicide Severity Rating Scales [C-SSRS] will be administered at each visit.)
- 4. Substance or alcohol abuse/dependence within previous 6 months, or a positive urine drug screen at screening or baseline prior to first dose of study medication (SM).
- 5. Any known or suspected significant medical or psychiatric illnesses that, in the judgment of the Investigator, may impair interpretation of study results or constitute a significant safety concern in the context of the clinical trial
- ECG abnormalities (clinically significant according to Investigator's opinion) or vital sign abnormalities (systolic blood pressure [SBP] <90 or >140 millimeters of mercury [mmHg], diastolic blood pressure [DBP] <40 or >90mmHg, or heart rate [HR] <40 or >100 beats per minute [BPM]) at screening.
- Clinically significant laboratory abnormalities; including presence of potential hepatic function impairment as shown by, but not limited to alanine aminotransferase (ALT) values >2 times upper limit of normal (ULN), aspartate aminotransferase (AST) > 2 times ULN, gamma-glutamyl transpeptidase (GGT) >3 times ULN, or total bilirubin >1.5 ULN.
- 8. Medications, including health food supplements judged by the Investigator to be likely to have central nervous system activity (for example, St John's Wort, gingko leaf, and melatonin), are not permitted during the study. If the subject is taking the medication prior to study entry, there must be a 7 day washout period prior to first dose of SM.
- 9. Lifetime history of tic disorder, Tourette's Disease, or organic brain disorder; or family history of Tourette's Disease.
- 10. Current or lifetime history of hyperthyroidism unless treated and stable for 6 months.
- 11. Participation in or plan to begin behavioral therapy during the study.
- 12. Subject has a prior history of allergy or any significant adverse reaction (including rash) to viloxazine, or any of the product components.
- 13. Females who are pregnant or lactating or are unwilling to use an acceptable form of contraception throughout the study.
- 14. Difficulty swallowing whole capsules.
- 15. History of seizures or risk factors for seizures (e.g., head trauma), not including febrile seizures.
- 16. Use of an investigational drug or participation in an investigational study within 30 days prior to first dose of SM.
- 17. Any reason which, in the opinion of the Investigator, would prevent the subject from participating in the study.

CONFIDENTIAL Version 2.0

### 9.4. Study Methods

### 9.4.1. Schedule of Visits and Procedures

Table 1. Schedule of Visits and Procedures presents the schedule of visits and procedures for the study.

Study Phase	Screening	Dose Treatment Period		End of Study b
	Period	(Visit window +/- 2 days)		
Activity	Visit 1 Up to 14 Days Prior to Visit 2	Visit 2	Visits 3 – 8	
Informed Consent a	Х			
Medical and Psychiatric History and Demographics	х			
Physical Exam	Х			Х
ECG (12-lead)	Х		Хc	Х
Vital Signs d	Х	Х	Х	Х
Hematology	Х			Х
Urinalysis and drug screen	Х			Х
CYP2D6 Enzyme Activity Screening	Х			
Serum Chemistry	Х			Х
Serum Pregnancy Test (for FOCP only)	х			Х
Urine Pregnancy Test (for FOCP only)		х		
CAADID	Х			
CGI	Х	Х	Х	Х
C-SSRS	Х	Х	Х	Х
CAARS e		Х	Х	Х
Concomitant Medication	Х	Х	Х	Х
Randomization		Х		
SM Dispensed		Х	Х	
SM Diary Dispensed			Xf	
Optional SM Administered On-Site g			х	
Optional PK Blood Sampling			X h	
Adverse Events			Х	Xi

a To be obtained prior to any study procedures being performed.

b To be performed at the end of Visit 8 (unless done previously during Visit 8), or at early discontinuation.

C At Visit 4 only

d Heart rate, seated blood pressure, temperature, and respiratory rate will be measured at every visit. The vital signs readings will be performed within approximately 10 minutes prior to the scheduled blood draws, where applicable. Height will be taken at screening and weight will be assessed at each visit.

e CAARS self-report done only at Visits 2 and 8, CAARS investigator-report done at Visits 2-8

 $f \qquad \mbox{At Visit 7 to record SM taken prior to Visit 8. \ \mbox{Diary to be collected at Visit 8}.$ 

- g Dose to be administered on-site after the pre-dose draw and an overnight fast at Visit 8; subjects may eat 2 hours after dosing.
- h At Visit 8, subjects who wish to participate will be dosed after an overnight fast and have a series of PK samples drawn. Samples will be taken pre-dose, and at Hours ½, 1, 2, 3, 4, 5, and 6.
- i Any subject who experiences an adverse event (whether serious or non-serious) or has a clinically significant abnormal laboratory test value(s) will be followed by the Investigator at appropriate intervals based on the severity and nature of the event, until resolved, or when the condition is assessed as stable, causality other than the SM has been found, or the subject is referred to another health care professional.

# 9.4.1.1. Screening Period

A Screening Period will take place within 14 days prior to the first dose administration to determine subjects' eligibility to participate in the study. If needed, screening may take place over more than 1 visit. Prior to conducting any screening procedures, written informed consent must be obtained from the subject.

The procedures to be performed will include:

- Informed consent process
- Medical and psychiatric history, including smoking history
- Demographics
- Administration of CAADID for confirmation of ADHD diagnosis
- Administration of CGI-S
- Administration of C-SSRS
- Assessment of inclusion/exclusion criteria
- Physical examination
- ECG (12-lead)
- Vital signs, height, and weight
- Laboratory tests (including hematology, clinical chemistry, and urinalysis)
- Urine drug screen
- Serum pregnancy test (for FOCP)
- Assessment of prior and concomitant medications

## 9.4.1.2. Baseline and Randomization

Once subjects have been adequately screened and it is determined the subject is eligible for the study, the subject will return for the baseline and randomization visit.

The procedures to be performed will include:

- Changes in medical and psychiatric history since last visit (AE collection starts after first dose)
- Administration of CGI-S
- Administration of CAARS, both investigator-rated and self-rated versions
- Administration of C-SSRS
- Vital signs and weight
- Urine pregnancy test (for FOCP)
- Assessment of concomitant medications
- Randomization

SM dispensed

## 9.4.1.3. Dose Treatment Period

### 9.4.1.3.1. Visits 2-7

Dosing Schedule:

- The first dose of SM should be taken the morning following the randomization visit.
- Following dosing for a week at the starting dose of 150mg SPN-812V or placebo (1 capsule TID), subjects will be titrated to and maintained at the 300mg SPN812-V or placebo dose level (2 capsules TID) for 5 weeks.
- Subjects in the highest dose group will be permitted to down titrate to the starting dose at the Investigator's discretion in consultation with the Medical Monitor. Subjects who still cannot tolerate study medication after one down-titration should be removed from the study. Visits will occur on a weekly basis (+/- 2 days).

The following evaluations will be performed:

- AEs assessed (monitoring begins after first dose of SM)
- Administration of CGI-I
- Administration of CAARS, investigator-rated version at each visit, self-rated version only at Visit 8
- Administration of C-SSRS
- Vital signs and weight
- ECG (12-lead) (Visit 4 only)
- Assessment of concomitant medications
- SM returned and dispensed, assessment of compliance
- SM time recordation diary dispensed to subjects who have consented to participate in the PK sub study (Visit 7)
- Subjects who will participate in the optional PK sub study at Visit 8 will be reminded to not eat or take SM prior to coming to the clinic the morning of Visit 8

### 9.4.1.3.2. Visit 8

The following evaluations will be performed:

- AEs assessed
- Administration of CGI
- Administration of CAARS, investigator-rated and self-rated versions
- Administration of C-SSRS
- Vital signs and weight

- Assessment of concomitant medications
- SM returned, assessment of compliance
- SM time recordation diary collected

PK Sub study Procedures: All efficacy assessments will be done first.

- Subjects who agree to participate in the optional PK sub study will be given 2 x 50mg SPN-812V on-site in the morning, unless the subject had been down-titrated, in which case, the subject will receive 1 x 50mg SPN-812V on-site in the morning.
- Subjects must arrive after an overnight fast and may eat two hours after dosing. The subject will have a pre-dose PK draw taken, will be dosed, and will have PK draws taken at ½, 1, 2, 3, 4, 5, and 6 hours post-dose. There is a 30 minute window on all draw times, but they may be used only so that there is at least one hour between each sampling time after the ½ hour post-dose draw.

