### 9.1.2. Dosing Period

Subjects who meet the requirements for study participation will be randomized and proceed to the Dosing Period which will last 6 weeks. Approximately 50 subjects will be randomized at a 1:1 ratio, using a centralized randomization system, to either SPN-812V or placebo. The first dose of SM should be taken the morning after the randomization visit.

At the baseline and randomization visit, baseline safety and efficacy assessments will be performed. Inclusion/Exclusion criteria should be re-assessed at this visit. Concomitant medication information will be collected. FOCP will be given a urine pregnancy test. SM will be dispensed.

Each week after randomization, subjects will return to the study site for monitoring of AEs, and the administration of safety tests and efficacy scales. Procedures to be performed are collection

CONFIDENTIAL Version 2.0

of vital signs and weight, PK blood sampling at Visit 8 (optional, if subjects wish to participate), and an ECG at Visit 4. Assessments of concomitant medications, suicide risk, and SM compliance and dispensation will be performed. Subjects who have consented to participate in the optional PK sub study will be given a diary at Visit 7 on which to record time of SM doses taken prior to Visit 8. Subjects who are participating in the optional PK sub study will be given all efficacy assessments prior to blood draws or dosing on the PK day. For subjects not participating in the optional PK sub study, their last dose will be taken the evening before the End of Study Visit (Visit 8).

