# 9.1.3. End of Study Visit/Early Termination

At the end of Visit 8, or prior to early discontinuation, subjects will undergo end of study assessments. AEs will be monitored, and safety tests and efficacy scales will be administered unless assessments were performed earlier in the visit. The procedures to be performed will include physical examination, collection of vital signs, weight, ECG, blood collection for hematology and chemistry, urine collection for urinalysis, drug screen, and pregnancy test (for FOCP). Assessments of concomitant medications and SM compliance will be performed.

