## 9.4.1.4. Final Visit/Early Termination

The following evaluations will be performed during the final visit or at early discontinuation (assessments completed at Visit 8 will not be repeated):

- Administration of CGI
- Administration of CAARS, investigator-rated version at Visits 2-8, self-rated version at Visit 8 only
- Administration of C-SSRS
- Physical examination
- ECG (12-lead)
- Vital signs and weight
- Laboratory tests (including hematology, clinical chemistry, and urinalysis)
- Urine drug screen
- Serum pregnancy test (for FOCP)
- Assessment of concomitant medications
- SM returned, assessment of compliance
- AEs assessed

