## 9.4.3. Pharmacokinetic Measurements

On the morning of Visit 8, all subjects who wish to participate in the optional PK day will arrive at the clinic after an overnight fast and will have all efficacy assessments administered first. The subjects then will have a pre-dose PK sample taken, and be administered either 2 x 50mg SPN-812V capsules or will be administered 1 x 50mg SPN-812V capsule for subjects who underwent dose reduction. PK sampling will occur pre-dose and at 0.5, 1, 2, 3, 4, 5, and 6 hours post-dose. Although there is a 30 minute window on draw times, efforts should be made to ensure that the time interval between any two sampling timepoints is not less than 30 minutes. Subjects may eat two hours after dosing.

SPN-812V concentrations in plasma samples will be determined by the Sponsor using a validated chromatographic method. The amount of blood to be drawn at each timepoint to determine the plasma concentrations of SPN-812V is 4mL. Information regarding sample collection, handling, and shipping procedures will be detailed in a separate manual.

Single dose administration of viloxazine hydrochloride (100mg) to ten healthy volunteers resulted in mean  $C_{max}$  near 1800 ng/mL for viloxazine at a mean  $T_{max} \sim 100$  min post-dose and with elimination half-life ~3 hr (Vandel B. et al., "Pharmacokinetics of viloxazine hydrochloride in man," European Journal of Drug Metabolism and Pharmacokinetics, 1982, Vol 7, pp. 65-68). Timepoints were chosen on the basis of these data to inform both absorption and elimination phases of the viloxazine time course while minimizing the sampling burden on patients. The design of the study provides both first-dose (in placebo group) and steady state (in active group) observations, albeit in parallel treatment groups.

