## 9.5. Treatments

#### 9.5.1. Treatments Administered

SM will be dispensed at each visit during the Randomization and Dose Treatment Periods. Subjects will receive a bottle at each visit containing the correct number of 50mg (or placebo) capsules, which is a sufficient number of capsules for dosing until the next visit. The SM will be taken by the subject orally, three times per day during waking hours, with at least 4 hours between doses (morning, noon, and evening).

At Visit 8, subjects who agree to participate in the optional PK sub study will be given 2 x 50mg SPN-812V capsules on-site in the morning, unless the subject had been down-titrated, in which case, the subject will receive 1 x 50mg SPN-812V capsule on-site in the morning. Note: all subjects who participate in the optional PK sub study will be given active SPN-812V capsule(s) in this portion. For subjects not participating in the optional PK sub study, their last dose will be taken the evening before the End of Study Visit (Visit 8).

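### Placebo-arm women who join the PK sub-study receive their first active dose about 42 days after their last required pregnancy test, with no negative result required beforehand

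*Protocol*

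**What the plan says.** **The dose.** Protocol 9.5.1 states that "all subjects who participate in the optional PK sub study will be given active SPN-812V capsule(s) in this portion". The amount is 2 x 50 mg, or 1 x 50 mg after down-titration. Section 9.4.3 makes clear that new exposure of placebo subjects is intended: "The design of the study provides both first-dose (in placebo group) and steady state (in active group) observations".

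**The order on the PK day.** Subjects arrive fasted. Section 9.4.1.3.2 then says "PK Sub study Procedures: All efficacy assessments will be done first", and a pre-dose PK sample precedes the dose. The Visit 8 procedure list in that section contains no pregnancy test.

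**The pregnancy tests.** Females of childbearing potential (FOCP) have a serum test at screening. At the baseline and randomization visit, "FOCP will be given a urine pregnancy test" (9.1.2). Nothing is listed for Visits 3 to 7. The last test belongs to the end-of-study assessments (Table 1 and 9.4.1.4). On their timing, 9.1.3 says "At the end of Visit 8, or prior to early discontinuation, subjects will undergo end of study assessments", and Table 1 footnote b says "To be performed at the end of Visit 8 (unless done previously during Visit 8), or at early discontinuation".

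**The order when dosing first starts.** The urine test is done at Visit 2, and "The first dose of SM should be taken the morning following the randomization visit" (9.4.1.3.1).

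**The concern.** The protocol tests FOCP just before the first planned exposure at the start of treatment. It does not do so before the other first exposure it creates, the PK dose given to placebo subjects. The Visit 8 test comes by default at the end of the visit, while PK sampling runs to 6 hours after the dose. A site following the text as written could therefore dose first and learn the pregnancy result afterwards.

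What is at stake is an avoidable first exposure of a woman with an unrecognised pregnancy. The dose is given after all efficacy ratings and serves only the PK sampling. The point concerns participant safety alone: no estimate, test or analysis population is affected. It makes no claim about the interval between tests in the active arm.

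**Working it through.** **1. Interval from the last required test to the first active dose, placebo arm**

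- Inputs: urine test at Visit 2 (9.1.2, 9.4.1.2); weekly visits with a window of +/- 2 days (9.4.1.3.1); PK dose on the morning of Visit 8 (9.4.1.3.2).
- Visit 2 to Visit 8 is 6 weekly intervals: 6 x 7 = **42 days**. This reproduces the 6-week Dosing Period in 9.1.2 (1 week at the starting dose plus 5 at the study dose: 7 + 35 = 42).
- With the window applied to Visit 8: 42 - 2 = 40 to 42 + 2 = 44 days.
- Sections 9.5.7 and 9.5.10 (Change of Study Medication Dose) instead describe 6 weeks of maintenance after titration. Read literally, that gives 7 + 42 = 49 days.

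**2. The same interval for women starting active drug after Visit 2**

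The test is at Visit 2 and the first dose the next morning: about **1 day**.

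**3. Is a result required between Visit 2 and the PK dose?**

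| Place in the Protocol | What it provides | Result required before the PK dose? |
|---|---|---|
| Table 1, 9.4.1.3.1 (Visits 3-7) | No pregnancy test | No |
| 9.4.1.3.2 (Visit 8 list and PK steps) | No pregnancy test | No |
| 9.4.3, 9.5.7 | Efficacy ratings before dosing; 9.4.3 adds fast and pre-dose sample | No |
| 9.1.3, 9.4.1.4, Table 1 footnote b | End-of-study test at the end of Visit 8, or earlier in the visit | Earlier is allowed, not required |
| 9.1.2 | Eligibility re-assessed at Visit 2 | No equivalent at Visit 8 |

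The remaining safeguards are contraception (inclusion criterion 9), withdrawal on pregnancy (9.4.5) and 24-hour reporting (9.4.4.2.2). The first lowers the risk. The other two act only on a pregnancy already known.

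**4. How many women**

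- Placebo completers at the planned 20% dropout (9.2): 25 x (1 - 0.20) = 20.
- Only FOCP who opt in are affected. The documents give neither share.
- Assumptions, for scale only: 5 to 10 such women, and a yearly pregnancy probability r of 1% to 10%.
- Probability over 42 days = 1 - (1 - r)^(42/365), which is 0.00116 at r = 1% and 0.01205 at r = 10%.
- Expected pregnancies: 5 x 0.00116 = 0.006 to 10 x 0.01205 = 0.12.

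This range counts every pregnancy arising in the 42 days. Those both unrecognised and detectable by urine test on the day are fewer, so under these assumptions it is an upper bound on what the fix would catch.

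**The case against.** **The standard looks selective.** An active-arm woman at full dose takes 7 x 150 + 35 x 300 = 11,550 mg over the same six weeks with no interim test. One 100 mg dose is under 1% of that. It is true that the protocol tolerates a long interval during continuous treatment. The placebo dose differs in being a first exposure, and before first exposure at Visit 2 the protocol does test.

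**The test may in practice come before the dose.** SAP 3.6.2 asks for fasting laboratory tests, and PK participants arrive fasted, so the end-of-study blood may well be drawn early. Footnote b allows this. But it governs when the sample is drawn, not when the result is known. Protocol 9.4.4.3 sends clinical laboratory tests to a central laboratory. If a serum pregnancy test goes there, an answer before dosing is not assured. Turnaround is not stated, so this last step is an assumption, and the main point does not depend on it.

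**The risk is small and its size is assumed.** Agreed. Contraception is required, and the pregnancy figures have no source in the documents. Contraception was also required before Visit 2, however, and the protocol still tested there.

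**Unseen documents may cover it.** The sub-study has its own consent form, and laboratory instructions are in a separate manual. Either could require a test. That limits any statement about what would happen at the sites, but not the reading of the protocol's own sequence.

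**An amendment is not free.** Under 10.3, a change affecting subject safety needs IRB approval, here for about 5 sites. This is a real administrative cost, though a modest one.

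**Conclusion.** The concern holds. For placebo-arm FOCP in the PK sub-study, the last test required before the first active dose is about 42 days old (40 to 44 with the visit window), against about 1 day for women starting active drug after Visit 2. The Visit 8 test is not tied to the dose.

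The number affected is small: some fraction of about 20 placebo completers. On the stated assumptions, at most 0.006 to 0.12 pregnancies would be expected. This is an improvement worth considering on grounds of safety and low cost. It is not a defect in the trial's inference. Confidence is high for the protocol and SAP wording; it does not extend to the PK consent form or site manuals, which were not available.

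**What to change.** In Protocol 9.4.1.3.2 and 9.4.3, require a urine pregnancy test with a negative result recorded before the on-site PK dose, for all FOCP in the sub-study. Apply it in both arms, because testing only placebo women would reveal the allocation. The interval from last required test to first active dose then falls from about 42 days to zero.

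Also state one test type for end of study. Protocol Table 1, 9.4.1.4 and SAP Table 1 say serum. Protocol 9.1.3 can be read as urine, and SAP Table 2 and the listings in SAP 6.2 name only urine. The extracted tables are imperfect, but the text of 9.1.3 and SAP 6.2 shows the same inconsistency.

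Cost: about two lines of amendment wording with IRB review, and a short wait before dosing. If serum is kept for end of study, add at most one urine test per participating woman; if the urine test replaces it, there is no extra test.
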